## 4.8 Rescue Medications & Supportive Care

### 4.8.1 Supportive Care Guidelines

Subjects should receive appropriate supportive care measures as deemed necessary by the treating investigator. Suggested supportive care measures for the management of adverse events with potential immunologic etiology are outlined below and in greater detail in the ECI guidance document. Where appropriate, these guidelines include the use of oral or intravenous treatment with corticosteroids as well as additional anti-inflammatory agents if symptoms do not improve with administration of corticosteroids. Note that several courses of steroid tapering may be necessary as symptoms may worsen when the steroid dose is decreased. For each disorder, attempts should be made to rule out other causes such as metastatic disease or bacterial or viral infection, which might require additional supportive care. The treatment guidelines are intended to be applied when the investigator determines the events to be related to pembrolizumab.

Note: if after the evaluation the event is determined not to be related, the investigator is instructed to follow the ECI reporting guidance but does not need to follow the treatment guidance (as outlined in the ECI guidance document). Refer to Section 5.2.1 for dose modification.

It may be necessary to perform conditional procedures such as bronchoscopy, endoscopy, or skin photography as part of evaluation of the event. Suggested conditional procedures, as appropriate, can be found in the ECI guidance document.

- **Pneumonitis:**

- For **Grade 2 events**, treat with systemic corticosteroids. When symptoms improve to Grade 1 or less, steroid taper should be started and continued over no less than 4 weeks.
- For **Grade 3-4 events**, immediately treat with intravenous steroids. Administer additional anti-inflammatory measures, as needed.
- Add prophylactic antibiotics for opportunistic infections in the case of prolonged steroid administration.

- **Diarrhea/Colitis:**

Subjects should be carefully monitored for signs and symptoms of enterocolitis (such as diarrhea, abdominal pain, blood or mucus in stool, with or without fever) and of bowel perforation (such as peritoneal signs and ileus).

- All subjects who experience diarrhea/colitis should be advised to drink liberal quantities of clear fluids. If sufficient oral fluid intake is not feasible, fluid and electrolytes should be substituted via IV infusion. For Grade 2 or higher diarrhea, consider GI consultation and endoscopy to confirm or rule out colitis.

- For **Grade 2 diarrhea/colitis** that persists greater than 3 days, administer oral corticosteroids.
- For **Grade 3 or 4 diarrhea/colitis** that persists > 1 week, treat with intravenous steroids followed by high dose oral steroids.
- When symptoms improve to Grade 1 or less, steroid taper should be started and continued over no less than 4 weeks.
- **Type 1 diabetes mellitus (if new onset, including diabetic ketoacidosis [DKA]) or ≥ Grade 3 Hyperglycemia, if associated with ketosis (ketonuria) or metabolic acidosis (DKA)**
  - For **T1DM** or **Grade 3-4 Hyperglycemia**
    - Insulin replacement therapy is recommended for Type I diabetes mellitus and for Grade 3-4 hyperglycemia associated with metabolic acidosis or ketonuria.
    - Evaluate patients with serum glucose and a metabolic panel, urine ketones, glycosylated hemoglobin, and C-peptide.
- **Hypophysitis:**
  - For **Grade 2** events, treat with corticosteroids. When symptoms improve to Grade 1 or less, steroid taper should be started and continued over no less than 4 weeks. Replacement of appropriate hormones may be required as the steroid dose is tapered.
  - For **Grade 3-4** events, treat with an initial dose of IV corticosteroids followed by oral corticosteroids. When symptoms improve to Grade 1 or less, steroid taper should be started and continued over no less than 4 weeks. Replacement of appropriate hormones may be required as the steroid dose is tapered.
- **Hyperthyroidism or Hypothyroidism:**

Thyroid disorders can occur at any time during treatment. Monitor patients for changes in thyroid function (at the start of treatment, periodically during treatment, and as indicated based on clinical evaluation) and for clinical signs and symptoms of thyroid disorders.

  - **Grade 2** hyperthyroidism events (and **Grade 2-4** hypothyroidism):
    - In hyperthyroidism, non-selective beta-blockers (e.g. propranolol) are suggested as initial therapy.
    - In hypothyroidism, thyroid hormone replacement therapy, with levothyroxine or liothyroinine, is indicated per standard of care.
  - **Grade 3-4** hyperthyroidism
    - Treat with an initial dose of IV corticosteroid followed by oral corticosteroids. When symptoms improve to Grade 1 or less, steroid

taper should be started and continued over no less than 4 weeks. Replacement of appropriate hormones may be required as the steroid dose is tapered.

- **Hepatic:**

- For **Grade 2** events, monitor liver function tests more frequently until returned to baseline values (consider weekly).
  - Treat with IV or oral corticosteroids
- For **Grade 3-4** events, treat with intravenous corticosteroids for 24 to 48 hours.
- When symptoms improve to Grade 1 or less, a steroid taper should be started and continued over no less than 4 weeks.

- **Renal Failure or Nephritis:**

- For **Grade 2** events, treat with corticosteroids.
- For **Grade 3-4** events, treat with systemic corticosteroids.
- When symptoms improve to Grade 1 or less, steroid taper should be started and continued over no less than 4 weeks.

- **Management of Infusion Reactions:** Signs and symptoms usually develop during or shortly after drug infusion and generally resolve completely within 24 hours of completion of infusion.

Table 4 below shows treatment guidelines for subjects who experience an infusion reaction associated with administration of pembrolizumab.

Table 4 Infusion Reaction Treatment Guidelines

NCI CTCAE Grade	Treatment	Premedication at subsequent dosing
Grade 1 Mild reaction; infusion interruption not indicated; intervention not indicated	Increase monitoring of vital signs as medically indicated until the subject is deemed medically stable in the opinion of the investigator.	None
Grade 2 Requires infusion interruption but responds promptly to symptomatic treatment (e.g., antihistamines, NSAIDS, narcotics, IV fluids); prophylactic medications indicated for <=24 hrs	Stop Infusion and monitor symptoms. Additional appropriate medical therapy may include but is not limited to: IV fluids Antihistamines NSAIDS Acetaminophen Narcotics	Subject may be premedicated 1.5h ( $\pm$ 30 minutes) prior to infusion of pembrolizumab with:  Diphenhydramine 50 mg po (or equivalent dose of antihistamine).  Acetaminophen 500-1000 mg po (or equivalent dose of antipyretic).

NCI CTCAE Grade	Treatment	Premedication at subsequent dosing
	
Increase monitoring of vital signs as medically indicated until the subject is deemed medically stable in the opinion of the investigator.
 
If symptoms resolve within one hour of stopping drug infusion, the infusion may be restarted at 50% of the original infusion rate (e.g., from 100 mL/hr to 50 mL/hr). Otherwise dosing will be held until symptoms resolve and the subject should be premedicated for the next scheduled dose.
 
Subjects who develop Grade 2 toxicity despite adequate premedication should be permanently discontinued from further trial treatment administration.
	
Grades 3 or 4	
Stop Infusion.
 
Additional appropriate medical therapy may include but is not limited to:
 
 
IV fluids
 
Antihistamines
 
NSAIDS
 
Acetaminophen
 
Narcotics
 
Oxygen
 
Pressors
 
Corticosteroids
 
Epinephrine
 
 
Increase monitoring of vital signs as medically indicated until the subject is deemed medically stable in the opinion of the investigator.
 
Hospitalization may be indicated.
 
Subject is permanently discontinued from further trial treatment administration.
	No subsequent dosing
Appropriate resuscitation equipment should be available in the room and a physician readily available during the period of drug administration.		

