### **4.7.2 Prohibited Concomitant Medications**

Subjects are prohibited from receiving the following therapies during the Screening and Treatment Phase (including retreatment for post-complete response relapse) of this trial:

- Antineoplastic systemic chemotherapy or biological therapy
- Immunotherapy not specified in this protocol
- Chemotherapy not specified in this protocol
- Investigational agents other than pembrolizumab
- Radiation therapy
  - Note: Radiation therapy to a symptomatic solitary lesion or to the brain may be allowed at the investigator's discretion.
- Live vaccines within 30 days prior to the first dose of trial treatment and while participating in the trial. Examples of live vaccines include, but are not limited to, the following: measles, mumps, rubella, varicella/zoster, yellow fever, rabies, BCG, and typhoid vaccine.
- Systemic glucocorticoids for any purpose other than to modulate symptoms from an event of clinical interest of suspected immunologic etiology. The use of physiologic doses of corticosteroids may be approved after consultation with Merck.

Subjects who, in the assessment by the investigator, require the use of any of the aforementioned treatments for clinical management should be removed from the trial. Subjects may receive other medications that the investigator deems to be medically necessary.

The Exclusion Criteria describes other medications which are prohibited in this trial.

There are no prohibited therapies during the Post-Treatment Follow-up Phase.

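### The written steroid trigger for diarrhea/colitis in section 4.8.1 runs against severity: more than 3 days at Grade 2, but more than 1 week at Grade 3 or 4

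*Combined protocol and SAP*

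**What the plan says.** The diarrhea/colitis part of section 4.8.1 has two steroid lines, one directly after the other. For moderate events: "For Grade 2 diarrhea/colitis that persists greater than 3 days, administer oral corticosteroids". For severe and life-threatening events: "For Grade 3 or 4 diarrhea/colitis that persists > 1 week, treat with intravenous steroids followed by high dose oral steroids".

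Other text bears on how these lines are used:

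- **Work-up.** The same part says: "For Grade 2 or higher diarrhea, consider GI consultation and endoscopy to confirm or rule out colitis". The opening of 4.8.1 adds: "For each disorder, attempts should be made to rule out other causes such as metastatic disease or bacterial or viral infection".
- **Status.** The measures are described as suggested, and "Subjects should receive appropriate supportive care measures as deemed necessary by the treating investigator". They apply to related events: "The treatment guidelines are intended to be applied when the investigator determines the events to be related to pembrolizumab".
- **Further source.** The measures are "outlined below and in greater detail in the ECI guidance document". Section 4.4.1.2 also sends the reader to that guidance for corticosteroid use, and section 9.4 lists it as a separate attachment.
- **Permission.** Section 4.7.2 prohibits "Systemic glucocorticoids for any purpose other than to modulate symptoms from an event of clinical interest of suspected immunologic etiology". Steroids for a suspected immune event are thus allowed, with no condition on how long the event has lasted.
- **Study drug.** For related colitis, Table 3 (section 4.4.1.2) holds pembrolizumab at Grade 2-3 and stops it permanently at Grade 4, with no waiting time.

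**The concern.** The written wait before steroids gets longer as the event gets worse. A clinician who takes the timing from this section would start steroids later in a patient with severe or life-threatening colitis than in one with moderate colitis. The same part of the section asks staff to watch for signs of bowel perforation, and Table 6 (section 6.2.4) describes Grade 4 as needing urgent action. A wait of more than a week that expressly includes Grade 4 does not fit either statement.

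What is at stake is patient safety in a Phase I trial whose primary objective is safety and tolerability. The point does not touch the primary endpoint, the sample size or the stopping rule.

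**Working it through.** The check is a comparison of two written triggers. The plan offers no figure of its own to reproduce.

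**Inputs, both from section 4.8.1, Diarrhea/Colitis**

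| Grade | Written trigger | Steroid |
|---|---|---|
| 2 | more than 3 days | oral |
| 3 or 4 | more than 1 week, i.e. more than 7 days | intravenous, then high-dose oral |

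**Difference.** Grade 3-4 wait minus Grade 2 wait = 7 − 3 = 4 days. Read literally, an event that has lasted more than 3 days but not more than 7 has a steroid instruction at Grade 2 and none at Grade 3 or 4.

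**Does the text explain the longer wait?**

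1. *Time to exclude infection.* The search for other causes is asked for in every disorder, and GI consultation and endoscopy are to be considered from Grade 2 upward without delay. Both grade groups have the same work-up, yet Grade 2 has the shorter wait. This cannot be the reason.
2. *Escalation to intravenous treatment after oral steroids.* The text does not say so. The oral line is limited to Grade 2, so a patient who presents at Grade 3 or 4 has no earlier written steroid step.
3. *A general pattern in the section.* Steroids are also suggested at Grade 3-4 for pneumonitis, hypophysitis, hyperthyroidism, hepatic events and renal events. None of these lines has a wait, and the pneumonitis line asks for immediate treatment. Colitis is also the only disorder with a wait at Grade 2, so this comparison does not itself prove the inversion. It does show that no other disorder in the section has a wait that grows with grade.

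**Effect of each correction**

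| Version | Grade 2 wait | Grade 3-4 wait | Grade 3-4 minus Grade 2 |
|---|---|---|---|
| As written | 3 days | 7 days | +4 days |
| One-week condition deleted | 3 days | 0 days | −3 days |
| Grade 3-4 wait capped at the Grade 2 wait | 3 days | at most 3 days | 0 or less |

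The documents give no colitis rate and no effect of delayed steroids. Neither the number of patients affected nor the harm can be estimated.

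**The case against.** The strongest reply is that the line binds nobody and is only a summary. The measures are suggestions, section 4.7 leaves the final decision on supportive therapy with the investigator or the patient's own physician, and section 4.7.2 allows steroids at any time for a suspected immune event. Nothing forbids treatment before day 7. Fluids, GI work-up and drug hold or discontinuation carry no wait. A hospitalized or life-threatening case is a serious adverse event that must reach the sponsor within 24 hours (section 6.2.3.1). Given the Table 6 definition of Grade 4, few clinicians would hold steroids for a week. The fuller ECI guidance is not in the text reviewed and may already set an earlier start. Deleting the condition could also be said to go too far, since it suggests intravenous steroids from day 0, possibly before endoscopy, in a trial where bowel radiation toxicity is a competing cause.

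Much of this stands, and it lowers the expected harm. It does not correct the line. Permission to treat earlier is not advice to do so. If the ECI guidance repeats the one-week trigger, both texts need correction. If it sets an earlier one, the protocol disagrees with the document it cites, and nothing in the text reviewed says which governs. The day-0 worry is met in part because the guidelines apply only once the investigator judges the event related to pembrolizumab, and in part by the 3-day option.

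**Conclusion.** The concern holds. As written, the steroid trigger is 4 days later for Grade 3-4 diarrhea/colitis than for Grade 2, and the document neither explains this nor cancels it. It should be fixed, on patient-safety grounds alone.

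Confidence is high for the wording. The conclusion assumes that the section is read literally and that the ECI guidance does not override it; the second point could not be checked. No delay in practice has been shown.

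**What to change.** Delete the one-week persistence condition from the Grade 3-4 diarrhea/colitis line in section 4.8.1, so that steroids are suggested once the event is judged related to pembrolizumab. At minimum, make any Grade 3-4 wait no longer than the Grade 2 wait of 3 days. Before the amendment is issued, confirm that the new wording agrees with the ECI guidance.

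The cost is one phrase in the next amendment and one check against that guidance. The downside is somewhat less time to exclude infection before steroids in Grade 3-4 events; the 3-day option keeps part of that time. No extra patients, visits or analyses are needed.

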## 4.9 Diet/Activity/Other Considerations

### 4.9.1 Diet

Subjects should maintain a normal diet unless modifications are required to manage an AE such as diarrhea, nausea or vomiting.

### 4.9.2 Contraception

Pembrolizumab may have adverse effects on a fetus in utero. Furthermore, it is not known if pembrolizumab has transient adverse effects on the composition of sperm. Non-pregnant, non-breast-feeding women may be enrolled if they are willing to use 2 methods of birth control or are considered highly unlikely to conceive. Highly unlikely to conceive is defined as 1) surgically sterilized, or 2) postmenopausal (a woman who is  $\geq 45$  years of age and has not had menses for greater than 1 year will be considered postmenopausal), or 3) not heterosexually active for the duration of the study. The two birth control methods can be either two barrier methods or a barrier method plus a hormonal method to prevent pregnancy. Subjects should

start using birth control from study Visit 1 throughout the study period up to 120 days after the last dose of study therapy.

The following are considered adequate barrier methods of contraception: diaphragm, condom (by the partner), copper intrauterine device, sponge, or spermicide. Appropriate hormonal contraceptives will include any registered and marketed contraceptive agent that contains an estrogen and/or a progestational agent (including oral, subcutaneous, intrauterine, or intramuscular agents).

Subjects should be informed that taking the study medication may involve unknown risks to the fetus (unborn baby) if pregnancy were to occur during the study. In order to participate in the study they must adhere to the contraception requirement (described above) for the duration of the study and during the follow-up period defined in section 7.2.2-Reporting of Pregnancy and Lactation to the Sponsor and to Merck. If there is any question that a subject will not reliably comply with the requirements for contraception, that subject should not be entered into the study.

#### **4.9.3 Use in Pregnancy**

If a subject inadvertently becomes pregnant while on treatment with pembrolizumab, the subject will immediately be removed from the study. The site will contact the subject at least monthly and document the subject's status until the pregnancy has been completed or terminated. The outcome of the pregnancy will be reported to the Sponsor and to Merck without delay and within 24 hours to the Sponsor and within 2 working days to Merck if the outcome is a serious adverse experience (e.g., death, abortion, congenital anomaly, or other disabling or life-threatening complication to the mother or newborn).

The study investigator will make every effort to obtain permission to follow the outcome of the pregnancy and report the condition of the fetus or newborn to the Sponsor. If a male subject impregnates his female partner the study personnel at the site must be informed immediately and the pregnancy reported to the Sponsor and to Merck and followed as described above and in Section 7.2.2.

#### **4.9.4 Use in Nursing Women**

It is unknown whether pembrolizumab is excreted in human milk. Since many drugs are excreted in human milk, and because of the potential for serious adverse reactions in the nursing infant, subjects who are breast-feeding are not eligible for enrollment.

### **4.10 Subject Withdrawal/Discontinuation Criteria**

Subjects may withdraw consent at any time for any reason or be dropped from the trial at the discretion of the investigator should any untoward effect occur. In addition, a subject may be withdrawn by the investigator or the Sponsor if enrollment into the trial is inappropriate, the trial plan is violated, or for administrative and/or other safety reasons. Specific details regarding discontinuation or withdrawal are provided in Section 7.1.4 – Other Procedures.

A subject must be discontinued from the trial for any of the following reasons:

- The subject or legal representative (such as a parent or legal guardian) withdraws consent.
- Confirmed radiographic disease progression

*Note:* A subject may be granted an exception to continue on treatment with confirmed radiographic progression if meeting the following criteria: 1) clinically stable, or 2) clinically improved, at the physician's discretion.

- Unacceptable adverse experiences as described in Section 5.2.1.2
- Intercurrent illness that prevents further administration of treatment
- Investigator's decision to withdraw the subject
- The subject has a confirmed positive serum pregnancy test
- Noncompliance with trial treatment or procedure requirements
- The subject is lost to follow-up
- Completed 24 months of uninterrupted treatment with pembrolizumab or 35 administrations of study medication, whichever is later.

*Note: 24 months of study medication is calculated from the date of first dose. Subjects who stop pembrolizumab after 24 months may be eligible for up to one year of additional study treatment if they progress after stopping study treatment provided they meet the requirements detailed in Section 7.1.5.5*

- Administrative reasons

The End of Treatment and Follow-up visit procedures are listed in Section 6 (Protocol Flow Chart) and Section 7.1.5 (Visit Requirements). After the end of treatment, each subject will be followed for 30 days for adverse event monitoring (serious adverse events will be collected for 90 days after the end of treatment as described in Section 7.2.3.1). Subjects who discontinue for reasons other than progressive disease will have post-treatment follow-up for disease status until disease progression, initiating a non-study cancer treatment, withdrawing consent or becoming lost to follow-up. After documented disease progression each subject will be followed by telephone for overall survival until death, withdrawal of consent, or the end of the study, whichever occurs first.

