#### **4.2.3 Rationale for Endpoints**

Given the lack of experience combining radiation therapy for MPM and immunotherapy, the primary endpoint will be high-grade toxicity, defined specifically in Table 3 below. Specifically, the Off-Study Criteria defined in Table 3 are the “Unacceptable” high-grade toxicities in the trial. That is, patients that meet these criteria will be considered as having met the study endpoint and will be taken off study. Patients will be monitored for 4 months after the start of RT. Since RT is approximately 1 month in duration, this monitoring period will include 3 months after the end of RT.

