### **6.1.1.5.3 Subsequent Anti-Cancer Therapy Status**

The investigator or qualified designee will review all new anti-neoplastic therapy initiated after the last dose of trial treatment. If a subject initiates a new anti-cancer therapy within 30 days after the last dose of trial treatment, the 30 day Safety Follow-up visit must occur before the first dose of the new therapy. Once new anti-cancer therapy has been initiated the subject will move into survival follow-up.

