#### **6.1.5.4 Follow-up Visits**

Subjects who discontinue trial treatment for a reason other than disease progression will move into the Follow-Up Phase and should be assessed every 6 weeks ( $42 \pm 7$  days) by radiologic imaging to monitor disease status. After 48 weeks the imaging time point will occur every 12 weeks ( $\pm 7$  days), up to 5 years. Every effort should be made to collect information regarding disease status until the start of new anti-neoplastic therapy, disease progression, death, end of the study or if the subject begins retreatment with pembrolizumab as detailed in Section 7.1.5.5. Information regarding post-study anti-neoplastic treatment will be collected if new treatment is initiated.

Subjects who are eligible to receive retreatment with pembrolizumab according to the criteria in Section 7.1.5.5 will move from the follow-up phase to the Second Course Phase when they experience disease progression. Details are provided in Section 6.2 – Trial Flow Chart for Retreatment.

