#### **6.1.5.4.1 Survival Follow-up**

Once a subject experiences confirmed disease progression or starts a new anti-cancer therapy, the subject moves into the survival follow-up phase and should be contacted by telephone every 12 weeks to assess for survival status until death, withdrawal of consent, or the end of the study, whichever occurs first.

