In addition to documenting all Grade 3 or higher toxicities during radiation therapy, all adverse events will be recorded from the time of study intervention (pembrolizumab) through 30 days following cessation of treatment and at each examination on the Adverse Event case report forms/worksheets. The reporting timeframe for adverse events meeting any serious criteria is described in section 7.2.3.1.

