### **7.2 Statistical Analysis Plan**

We will enroll a total of 24 patients, twelve patients to each cohort consisting of distinct radiation and immunotherapy treatment plans. For each study cohort, treatment-related toxicity is defined in Table 3 above (in the column “Discontinue Treatment/Off-Study Criteria”. Therefore, any patient meeting this criteria will be deemed to have experienced an “unacceptable” toxicity for the purposes of the trial. For each study condition, we plan to enroll 12 patients in cohorts of size 6. All patients will be monitored for at least 4 months from the beginning of RT, before declaring the treatment acceptable for enrolling the next cohort of 6 patients.

Continuous monitoring using the method of Thall [20] will be employed for each study cohort of 12 patients in cohorts of size 6 where each patient is monitored for at least 4 months from the start of RT. We will stop the trial if we have reason to believe that the treatment-related toxicity rate is more than 30%. Using the following probability rule

$$\Pr(\text{rate of treatment-related toxicity 4 months from the start of RT} > 30\% \mid \text{data}) > 0.80.$$

If we determine there is more than a 80% chance that the treatment-related toxicity rate is more than 30%, we will stop the trial. We will assume a beta(0.6, 1.4) distribution for treatment-related toxicity as this prior provides a mean of 30% and a standard deviation of 26.5%. Thus the trial will be stopped if

$$[\# \text{ of patients with treatment-related toxicity 4 months from day 1 of the start of RT} / \# \text{ of patients evaluated}]$$

$$\geq 3/6, 6/12$$

Therefore, we will stop either study cohort if we observe 3 or more treatment-related toxicities in the first 6 patients, or if we observe 6 treatment related toxicities at any time while evaluating all 12 patients. We will suspend accrual while evaluating the first 6 patients to ensure none of

the stopping boundaries have been reached prior to enrolling the final 6 patients of each study cohort. The operating characteristics from this decision rule are shown in Table X and are based on 1000 simulations for each scenario.

Table X. Operating characteristics for toxicity monitoring rule

Treatment-related Toxicity 4 months after start of RX	Probability of Stopping Early	Sample Size Avg
0.10	0.017	11.9
0.20	0.099	11.4
0.30	0.254	10.5
0.40	0.462	9.2
0.50	0.650	8.1

- Operating Characteristics acquired using the Stata command stopbound

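### For patients who stop early, routine adverse event recording can end before the 4-month window that the primary toxicity endpoint and stopping rule count

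*Combined protocol and SAP*

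**What the plan says.** **The endpoint window.** Section 4.2.3 makes the off-study toxicities of Table 3 the primary endpoint and states: "Patients will be monitored for 4 months after the start of RT". Section 7.2 makes this a minimum for everyone, to be met before the next six patients enter: "All patients will be monitored for at least 4 months from the beginning of RT". A cohort stops at 3 or more events in the first 6 patients, or at 6 events among the 12.

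**The recording period.** Section 4.10: "After the end of treatment, each subject will be followed for 30 days for adverse event monitoring". Section 6.2: "all adverse events will be recorded from the time of study intervention (pembrolizumab) through 30 days following cessation of treatment"; that sentence also calls for recording at each examination. Section 6.1.2.1 says grading and recording go on during follow-up. Section 6.1.5.3 puts the safety visit about 30 days after the last dose, or sooner if a new anti-cancer treatment is about to start. The flow chart in section 5.1 counts the 30 days from discontinuation.

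**Contact afterwards.** It depends on why the patient stopped.
- Other than progression (section 6.1.5.4): "Subjects who discontinue trial treatment for a reason other than disease progression will move into the Follow-Up Phase", with imaging every 6 weeks.
- Progression (section 4.10): "After documented disease progression each subject will be followed by telephone for overall survival until death".
- Progression or new therapy (section 6.1.5.4.1): "Once a subject experiences confirmed disease progression or starts a new anti-cancer therapy, the subject moves into the survival follow-up phase". Contact there is a telephone call every 12 weeks about survival.
- New therapy (section 6.1.1.5.3): "Once new anti-cancer therapy has been initiated the subject will move into survival follow-up".

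**Longer capture for some events.** Serious adverse events are collected to 90 days after the last study treatment (section 6.2.3.1). Events of clinical interest (ECIs) are collected to 90 days after cessation, or to 30 days after new therapy if that is earlier (section 6.2.3.2). Events above Grade 1 found by the safety visit are followed until they resolve or new therapy starts (section 6.1.5.3).

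**The concern.** The endpoint clock starts with RT, while the recording clock stops relative to the end of treatment. For most patients the second outlasts the first. For a patient on a short palliative course who progresses at the first on-treatment scan, it may not, and that patient has no scheduled toxicity contact up to month 4.

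The 4-month count decides whether each cohort goes past six patients. An event that is not recorded can only lower the count, so the error runs one way, towards continuing. One event can decide the first look. With the beta(0.6, 1.4) prior, the posterior probability that the rate exceeds 30% is 0.800 at 3/6 and 0.523 at 2/6.

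**Working it through.** **The plan's own figure.** Section 7.2 gives a 0.650 chance of stopping early at a true rate of 0.50. The exact chance of at least 3 events in 6 is 1 − (1 + 6 + 15)/64 = 0.656. The difference is within the error of 1000 simulations, whose standard error is √(0.65 × 0.35/1000) ≈ 0.015. The rule is as stated; the question is what feeds it.

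**Inputs for the timeline**, in weeks from the first RT fraction:
- Cohort 2 courses of 5, 10 or 15 fractions and Cohort 1 courses of 25 (section 4.4.4.3): 1, 2, 3 and 5 weeks, assuming 5 fractions a week.
- Pembrolizumab starts within 1 month of the end of RT, with no minimum stated (section 4.4). I use 0, 0.5 and 1 month: 0, 2.17 and 4.35 weeks.
- Dosing is every 3 weeks and the scan follows cycle 3 (sections 4.4.2 and 6.1.2.6). With C the week of dose 1, dose 3 falls at C + 6 and the scan at C + 9.
- 30 days = 4.29 weeks, 90 days = 12.86 weeks, 4 months = 17.4 weeks.

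**Shortfall before month 4**, set to zero if negative:
- from the last dose: 17.4 − (C + 6 + 4.29)
- from discontinuation at the scan: 17.4 − (C + 9 + 4.29)

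Weeks lost, for a start 0 / 0.5 / 1 month after RT:

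| RT course | From last dose | From discontinuation |
|---|---|---|
| 5 fractions | 6.1 / 3.9 / 1.8 | 3.1 / 0.9 / 0 |
| 10 fractions | 5.1 / 2.9 / 0.8 | 2.1 / 0 / 0 |
| 15 fractions | 4.1 / 1.9 / 0 | 1.1 / 0 / 0 |
| 25 fractions (Cohort 1) | 2.1 / 0 / 0 | 0 / 0 / 0 |

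A count in days agrees. With 5 weekday fractions and dose 1 the day after, dose 3 is on day 47 and recording from the last dose ends on day 77, which is 45 days short of day 122. Counted from discontinuation on day 68, it ends on day 98, 24 days short.

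**What is still captured.** For a stop at this scan, serious events run to C + 6 + 12.86 = C + 18.86, so to week 19.9 at the earliest, past month 4 in every schedule. ECIs also cover the window unless new therapy starts. If it starts at the scan, ECI capture ends at C + 13.29, week 14.3 at the earliest, or 3.1 weeks short.

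**Illustration of the effect on the rule.** The documents do not give the inputs, so these are assumptions: a share g of patients stops at this scan, they lose a fraction f of the window, a share s of their events is neither serious nor an ECI, and events are uniform over the window. The observed rate is then q = p(1 − g·f·s). Take p = 0.50, f = 2.9/17.4, s = 0.5 and g = 0.24. The value of g is prompted only by the 76% disease control in section 4.1, which comes without RT or scan timing.
- q = 0.50 × (1 − 0.02) = 0.490
- events missed per 12 patients: 12 × 0.010 = 0.12
- chance of 3 or more in 6: 0.637, against 0.656
- for g from 0.10 to 0.40: 0.05 to 0.20 events missed, chance 0.648 to 0.625

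**The case against.** The strongest reply is that section 7.2 already requires 4 months of monitoring and holds the next six patients until it is complete, while sections 6.1.2.1 and 6.2 extend recording into follow-up and to each examination. On that reading section 4.10 merely lacks a cross-reference. This stands in part: the plan states the right window, and data loss is not certain. But neither clause schedules a toxicity contact for a progressor, whose only planned contact is a survival call.

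The timing can also be read more kindly. Sections 4.10, 5.1 and 6.2 refer to the end or cessation of treatment, or to discontinuation; only section 6.1.5.3 names the last dose. Progression must be confirmed, and a clinically stable or improved patient may continue (section 4.10). If dose 4 is given while confirmation is awaited, the last-dose count also falls to at most 3.1 weeks. That stands, and it is why both ranges are given.

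Finally, the exposed class is narrow. Section 6.2.4 links Grade 3 with hospitalisation, which would make many such events serious. That row also lists severe or disabling events, however, so a new Grade 3 radiation esophagitis managed without admission would count under Table 3 and yet could be neither serious nor an ECI.

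A reader might infer that the stopping rule is badly weakened. With 6.1 weeks lost by every such patient and nothing captured, the illustration gives a stopping chance of 0.574. The documents do not support that, because serious events are collected throughout the window in this scenario.

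**Conclusion.** The mismatch is in the current text and is worth correcting. For a Cohort 2 patient stopped at the scan after cycle 3, routine recording falls short of month 4 by 0 to about 3 weeks counted from discontinuation, or 0 to about 6 weeks from the last dose. The maximum needs a 5-fraction course and pembrolizumab right after RT. The events at risk are mainly new Table 3 toxicities that are neither serious nor ECIs.

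The effect on the stopping rule is likely small, and its direction is known: towards continuing. Its size cannot be derived from the documents. The share of early stoppers is not given, and the ECI guidance document (section 9.4) is not included, so the proportion of immune events covered is unknown. The figure of 0.637 is an illustration only.

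A reader might also infer that early stoppers without an event should be replaced. The documents do not support that step. Section 7.2 refers to evaluable subjects without settling this case. Counting patients with events at once while replacing event-free early stoppers would push the observed rate up and could take enrolment above 24.

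**What to change.** - **Sections 4.10 and 6.2:** replace the 30-day limit with a rule that all adverse events are recorded, and graded against Table 3, until the later of 30 days after the last pembrolizumab dose and 4 months from the start of RT, regardless of progression or new therapy. This also settles which date the 30 days run from.
- **Sections 4.10, 6.1.1.5.3 and 6.1.5.4.1:** state that survival-only follow-up begins no earlier than the end of that recording period.

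The cost is one month-4 toxicity contact for the few patients who stop early. If 10% to 40% of a cohort stop at the first scan (an assumption), that is about 1 to 5 of 12 patients. Events arising after a new therapy starts will be harder to attribute, which matters because Table 3 counts only treatment-related toxicity.
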